5. METHODS

This study is planned to be carried out as a prospective application study in a pre-operative clinic. Adult patients planned to undergo pre-operative examination and evaluation by an anaesthesiologist for elective surgery are to be included (see paragraph 5.1. for full inclusion and exclusion criteria).

Included patients will be evaluated by an anaesthesiologist according to national and international guidelines as it is routine at the pre-operative clinic. In addition, all included patients will have their Hb measured non-invasively by a trained health care provider. SpHb values will be recorded in the documentation software already in use at the clinic.

5.1. Inclusion and exclusion criteria

Inclusion criteria

- Age \geq 18 years
- Patient planned for elective surgery
- Patient undergoing pre-operative evaluation by an anaesthesiologist
- Informed consent

Exclusion criteria

- Age $<$ 18 years
- Patient refusal

- Emergency surgery
- No central laboratory Hb test available

5.2. Data acquisition

Routine documentation of the anaesthesiologic evaluation will be performed by clinical staff in the pre-operative clinic using the software solution already in clinical use.

Study relevant data including SpHb, invasively measured Hb and general patient information, will be extracted from the hospital's documentation programme already used in the pre-operative clinic.

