1. TABULAR SUMMARY

Aim	
 • Anaemic patients that otherwise undetected by pre-operative tests recommended by international guidelines • Accuracy of SpHb compared to the gold standard in a pre-operative setting
Endpoints	
 • SpHb measurement pre-operatively • Laboratory Hb measurement pre-operatively • n of detected anaemic patients • n of otherwise (according to pre-operative blood sampling guidelines) undetected anaemic patients
Inclusion criteria	
 • Age > 18 years • Patient is planned for elective surgery • Pre-operative evaluation by an anaesthesiologist • Informed consent
Exclusion criteria	
 • Age <18 years • Patient refusal • Emergency surgery • No central laboratory Hb-test available
Sample size	Approximately 1500 patients
Study site	Div. of General Anaesthesiology, Emergency- and Intensive Care Medicine, Medical University of Graz
Sponsor	
Medical University of Graz
 
Div. of Gen. Anaesthesiology, Emergency- and Intensive Care Medicine, Medical University of Graz, Austria
 
Head: [name], MD, PhD

Investigator	
[name]
 
Div. of Gen. Anaesthesiology, Emergency- and Intensive Care Medicine, Medical University of Graz, Austria

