6. STATISTICAL CONSIDERATIONS

6.1. Sample size

The sample size was calculated based on a two-sided confidence interval with a confidence level $1-\alpha$ of 95%, an expected proportion of 0,85 and a distance of proportion to limit of 0,05.

With a prevalence of 14,1%(11) in a pre-operative setting for anemia the sample size needed was calculated to be 1392.

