6.2. Statistical analyses

Mean differences and standard deviation (SD) will be calculated. Accuracy (trueness and precision) of non-invasive Hb measurement will be compared with its gold standard using linear regression analysis and Bland-Altman-analysis.

Potential SpHb cut-offs to reliably non-invasively detect anaemia as defined by the gold-standard will be tested using receiver-operating characteristics (ROC) analysis.

The theoretical number of patients with anaemia that would remain undetected by strict application of existing guidelines concerning preoperative laboratory measurements will be expressed as a total amount within the patient cohort and as an incidence per 100.000 patients.

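### No rule covers a failed SpHb reading, so cut-off performance will by default describe readable patients rather than all patients in whom the pre-test is attempted

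*Combined protocol and SAP*

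**What the plan says.** Section 5 (Methods) plans that "all included patients will have their Hb measured non-invasively by a trained health care provider", and that the resulting values go into the clinic's existing software. Section 5.2 then states: "Study relevant data including SpHb, invasively measured Hb and general patient information, will be extracted from the hospital's documentation programme". Section 5.3 puts these data in a spreadsheet with one line per patient. None of these sections mentions recording an attempt that yields no value, or the quality of a reading.

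The only rule for a missing measurement concerns the reference test. Section 5.1 lists as an exclusion "No central laboratory Hb test available". There is no counterpart for a missing SpHb.

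Section 6.2 plans mean difference and SD, linear regression and Bland-Altman analysis for agreement. For the cut-offs it says: "Potential SpHb cut-offs to reliably non-invasively detect anaemia as defined by the gold-standard will be tested using receiver-operating characteristics (ROC) analysis". It defines no analysis population and no handling of missing or indeterminate SpHb results. It also plans a count of anaemic patients whom strict use of existing guidelines would miss.

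The endpoints in the tabular summary are the two Hb measurements and two counts of anaemic patients. None concerns failed readings.

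**The concern.** A patient whose probe gives no valid reading is still eligible and still has a laboratory Hb, but cannot enter a regression, a Bland-Altman plot or a ROC curve. Unless the plan says otherwise, those analyses are complete-case analyses of readable patients.

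That matters for research question 1, which asks whether SpHb can serve as a pre-test for patients who would normally have no laboratory test. In that use a failed reading is a result with a consequence: either anaemia goes undetected, or a laboratory test is done after all. Cut-off performance confined to readable patients leaves both consequences out. The first alternative hypothesis in Section 4.2 also claims that SpHb is easy to use, and no planned measure would show how often it fails.

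Timing adds to the problem. If only values are captured, failed attempts may not be recoverable once recruitment has ended.

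**Working it through.** **Inputs from the documents.** Section 6.1: "The sample size was calculated based on a two-sided confidence interval", with a confidence level "of 95%, an expected proportion of 0,85 and a distance of proportion to limit of 0,05"; and "With a prevalence of 14,1%(11) in a pre-operative setting for anemia the sample size needed was calculated to be 1392". Tabular summary: "Approximately 1500 patients".

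**Assumptions.** Section 6.1 does not name the proportion 0.85. It is read here as sensitivity, because the result is scaled up by anaemia prevalence. The documents give no failure rate f, so 2%, 5% and 10% are used, equal in anaemic and non-anaemic patients. A specificity of 0.85 is also assumed.

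**Step 1: reproduce the plan's figure.**
- Anaemic patients: 1.96² × 0.85 × 0.15 / 0.05² = 195.9, rounded up to 196.
- Total: 196 / 0.141 = 1390.1, rounded up to 1391, against 1392 stated.

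The figure is reproduced to within one patient with no allowance for failed readings.

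**Step 2: move from readable patients to all attempted patients.**
- Rule A, failure counted as not detected: sensitivity = 0.85 × (1 − f); specificity = 0.85 × (1 − f) + f.
- Rule B, failure counted as needing a laboratory test: sensitivity = 0.85 × (1 − f) + f; specificity = 0.85 × (1 − f).

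| f | A: sensitivity | A: specificity | B: sensitivity | B: specificity |
|---|---|---|---|---|
| 0 | 0.850 | 0.850 | 0.850 | 0.850 |
| 2% | 0.833 | 0.853 | 0.853 | 0.833 |
| 5% | 0.808 | 0.858 | 0.858 | 0.808 |
| 10% | 0.765 | 0.865 | 0.865 | 0.765 |

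With equal failure rates, the Youden index (sensitivity + specificity − 1) falls by the factor 1 − f under either rule. At 10% it goes from 0.70 to 0.765 + 0.865 − 1 = 0.63.

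**Step 3: compare with the planned precision.** The drop in the affected measure is 0.85 × f: 0.017, 0.0425 and 0.085. It reaches the planned half-width of 0.05 at f = 0.05 / 0.85 = 5.9%.

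**Step 4: is this a sample size problem?** Enrolling 1500 leaves 1392 readable patients up to f = 1 − 1392 / 1500 = 7.2%. At f = 10%, the readable anaemic patients number 1500 × 0.141 × 0.90 = 190.4, and the half-width is 1.96 × √(0.85 × 0.15 / 190.4) = 0.0507. Precision is hardly affected; the issue is who is analysed.

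**The case against.** The best defence has five parts.

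- **Everyone is to be measured.** Section 5 says so, and specifies a trained provider. That states an intention. It does not say what is recorded or analysed when the probe gives no valid reading.
- **Failures may be rare.** This stands. With no failures the effect is zero, and at 2% it is 0.017. But the plan would not show that they are rare, because it does not ask for them to be recorded.
- **Unreadable patients might simply have a laboratory test.** The documents state neither this nor the opposite. A reader might infer that sensitivity is necessarily inflated; the documents do not support that. Under Rule B sensitivity is slightly higher among all attempted patients, and what is overstated is specificity and the number of laboratory tests avoided. Even the net loss can reverse: under Rule B the Youden index changes by 0.15 × fₐ − 0.85 × fₙ, where fₐ and fₙ are the failure rates in anaemic and non-anaemic patients. The change is positive only if fₐ / fₙ exceeds about 5.7.
- **These patients still count somewhere.** A reader might infer that they disappear from the study. They do not. As Section 6.2 words it, the count of anaemia missed by guidelines rests on laboratory Hb and guideline indication, so a patient with a failed reading can contribute.
- **Agreement is not shown to be biased.** This also stands. Mean difference, SD and limits of agreement exist only for paired values and remain valid for readable patients. What is in question is how far they generalise.

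The documents do not describe the software's data fields. That a failed attempt would look the same as one never made is therefore a risk, not an established fact. They also give no ground for assuming that failures are commoner in anaemic patients.

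**Conclusion.** The gap is real and bears on the main research question. The plan covers a missing laboratory Hb but not a failed SpHb reading, and its SpHb analyses will by default describe readable patients only.

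Its size cannot be determined from the documents. On the assumptions above, the affected measure falls from 0.85 to 0.83, 0.81 and 0.77 at failure rates of 2%, 5% and 10%. At 5% the gap is still a little below the planned half-width; from about 6% it exceeds it. Which measure is affected depends on a counting rule that the plan has not stated.

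It should be corrected because the remedy is cheap and the information may be lost if it is not captured during recruitment. It does not call for a larger sample.

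**What to change.** **Section 5.2.** For every enrolled patient, record one of three entries: an SpHb value; *attempted, no valid reading*; or *not attempted*. If the clinic software cannot take the extra code, enter it in the study data sheet described in Section 5.3, noted at the time of measurement.

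**Section 6.2.**
- Report the proportion of failed readings with a 95% confidence interval, overall and by laboratory anaemia status.
- Report cut-off sensitivity and specificity among all attempted patients twice: once with failures counted as not detected, once with failures counted as needing a laboratory test.
- Keep Bland-Altman, regression and ROC as planned, and label them as based on valid readings.

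**Cost.** Slightly more documentation per patient and a few extra rows in the results. The stated performance may be less favourable. The documents do not say whether the clinical software can be changed, which is why the data sheet is offered as an alternative.

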5.3. Data management and Confidentiality

All study related data will be collected in a Microsoft Excel[®] data sheet. Individual patients will be represented by single data lines only.

Datasets will be encoded by numeric identifiers (pseudonymisation) already in use at the institution (admission number).

All analyses will be performed, using this pseudonymized dataset, in IBM SPSS Statistics[®] 23 provided by the Medical University of Graz.

6. STATISTICAL CONSIDERATIONS

6.1. Sample size

The sample size was calculated based on a two-sided confidence interval with a confidence level $1-\alpha$ of 95%, an expected proportion of 0,85 and a distance of proportion to limit of 0,05.

With a prevalence of 14,1%(11) in a pre-operative setting for anemia the sample size needed was calculated to be 1392.

6.2. Statistical analyses

Mean differences and standard deviation (SD) will be calculated. Accuracy (trueness and precision) of non-invasive Hb measurement will be compared with its gold standard using linear regression analysis and Bland-Altman-analysis.

Potential SpHb cut-offs to reliably non-invasively detect anaemia as defined by the gold-standard will be tested using receiver-operating characteristics (ROC) analysis.

The theoretical number of patients with anaemia that would remain undetected by strict application of existing guidelines concerning preoperative laboratory measurements will be expressed as a total amount within the patient cohort and as an incidence per 100.000 patients.

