All patients will be evaluated pre-operatively by an anaesthesiologist, utilizing both central laboratory measurements as clinical routine and non-invasive Hb measurements. Both measurements (SpHb and central laboratory Hb) will be documented, along with the normally collected patient data, using the electronic system currently in use. Median values from the two methods will be compared, and possible cut-off values calculated.

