3.2. Non-invasive haemoglobin measurement

Haemoglobin assessment is one of the most common laboratory tests performed worldwide. The value of a reliable clinical method of measure Hb in patients undergoing major surgery is well established. (4, 10)

The gold standard of Hb measurement involves venepuncture or finger prick. These methods are invasive and costly in terms of both time and resources, not to mention the risk they pose for both patient and clinical staff. These risks include pain, nerve damage, infection and the transmission of diseases.

Non-invasive Hb measurement is performed with a finger probe to measure SpHb without blood sampling. Rad-67™ Spot-check Pulse CO-Oximeter® (Masimo corporation, Irvine,

CA) is a device based on multi-wavelength co-oximetry for the spectrophometric estimation of haemoglobin (SpHb).

The usefulness of continuously measuring SpHb in a perioperative setting has previously been described. Several studies have shown that SpHb can help to estimate Hb values in various settings and to reduce unnecessary red blood cell (RBC) transfusions. It is also useful for Hb trend monitoring during surgery. (2, 12-14)

A meta-analysis by Kim et. al showed that the overall pooled random-effects mean difference (non-invasive vs. central laboratory) and SD were 0.10 ± 1.37 g/dL (-2.59 to 2.80 g/dL, I = 95.9% for mean difference and 95.0% for SD). (2)

In a pre-operative setting SpHb could act as an additional tool to reduce unnecessary testing without the cost of overlooking anaemic patients.

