4. AIM OF THE STUDY

This studies aim is to evaluate the accuracy of non-invasive Hb measurement in a pre-operative setting and its possible role in a PBM approach to detect anaemic patients before surgery.

We will compare SpHb to the gold standard and seek to establish cut-off values that could be used to identify patients that need laboratory Hb measurement irrespective of physical status preoperatively.

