4.1. Research questions

Research question 1: Can we use non-invasive Hb measurement as a pre-test to detect patients that are anaemic but would normally not get a central laboratory test?

Research question 2: Can we establish cut-off values for SpHb in a pre-operative setting?

Research question 3: How accurate is SpHb in a pre-operative setting for patients undergoing different kinds of surgery compared to the gold standard?

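### The SpHb cut-off is to be chosen and evaluated on the same patients, with no selection rule, no interval for sensitivity and no correction; under an optimum-seeking rule sensitivity would be overstated by about 1 to 2 points on average

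*Combined protocol and SAP*

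**What the plan says.** Section 6.1 (Sample size) uses a "two-sided confidence interval with a confidence level" of 95%, with "an expected proportion of 0,85 and a distance of proportion to limit of 0,05", and scales by an anaemia prevalence of 14.1% to reach 1392 patients. It does not say which proportion the 0.85 is. Section 1 rounds enrolment to about 1500.

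The cut-off is an output of this cohort. Section 2 (Summary) says that both Hb values will be recorded "and possible cut-off values calculated". Section 4 states that the investigators "seek to establish cut-off values that could be used to identify patients that need laboratory Hb measurement". Section 4.1 asks: "Research question 2: Can we establish cut-off values for SpHb in a pre-operative setting"?

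The only method given for this is in section 6.2: "Potential SpHb cut-offs to reliably non-invasively detect anaemia as defined by the gold-standard will be tested using receiver-operating characteristics (ROC) analysis". No section gives a rule for picking a point on the ROC curve, a pre-specified cut-off, a split sample, cross-validation, a bootstrap or a validation cohort. Section 6.2 does not mention sensitivity or an interval for it.

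**The concern.** The precision formula in 6.1 allows only for binomial error at a cut-off fixed independently of the patients counted. When the cut-off is chosen because it performs best in those patients, its observed sensitivity is too high on average, and the usual interval covers the truth less often than stated. Also, the ±0.05 in 6.1 has no matching result in 6.2.

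The cut-off is meant to show who should go on to a laboratory Hb, and its sensitivity is the share of anaemic patients it finds. An optimistic value makes the pre-test look safer than it is, and a reader of the results could not see this. With no rule on paper, the choice can also be made after the curve has been seen.

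**Working it through.** **1. The plan's own figure.** Inputs from 6.1: z = 1.96, proportion 0.85, half-width 0.05, prevalence 0.141.

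- 1.96² × 0.85 × 0.15 / 0.05² = 195.9, so 196 patients.
- 196 / 0.141 = 1390, against 1392 stated: reproduced within rounding.
- Check: 1392 × 0.141 = 196.3, and 1.96 × √(0.85 × 0.15 / 196) = 0.050.

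Since 196 is divided by the prevalence of anaemia, the 0.85 is a proportion among anaemic patients, that is, sensitivity. This is an inference. The 1392 and the 14.1% are taken as planned.

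**2. Optimum-seeking rules.** Each simulated study has N = 1392 and a random anaemic count at 14.1%. The cut-off is chosen in the sample. Overstatement is the observed sensitivity minus the true sensitivity at that same cut-off. Settings:

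- A: two normal SpHb distributions with sensitivity and specificity both 0.85 at the optimum.
- B: SpHb = Hb + error, with the error taken from section 3.2 ("mean difference (non-invasive vs. central laboratory) and SD were 0.10 ± 1.37 g/dL") and Hb normal with an assumed SD of 1.3, 1.6 or 2.0 g/dL.

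Youden rule, 5000 studies per setting:

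| | A | B, SD 1.3 | B, SD 1.6 | B, SD 2.0 |
|---|---|---|---|---|
| Continuous SpHb: overstatement (points) | 1.7 | 2.1 | 1.9 | 1.7 |
| Wald coverage | 0.875 | 0.869 | 0.872 | 0.869 |
| Wilson coverage | 0.921 | 0.909 | 0.915 | 0.920 |
| SpHb to 0.1 g/dL: overstatement (points) | 1.2 | 1.6 | 1.6 | 1.4 |
| Wald coverage | 0.907 | 0.898 | 0.897 | 0.885 |
| Wilson coverage | 0.939 | 0.931 | 0.936 | 0.932 |

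Exact intervals covered 0.916-0.929 (continuous) and 0.938-0.944 (0.1 g/dL). Other normal models, including unequal variances and smaller SpHb error, widen the overstatement to 1.0-2.2 points. Specificity is overstated by only 0.1-0.4 points. Closest-to-corner gives 1.3-1.5 points (continuous) or 0.8-1.1 (0.1 g/dL).

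**3. Pre-stated sensitivity target.** If the cut-off is the k-th lowest SpHb among 196 anaemic patients, true sensitivity follows Beta(k, 197 − k), with mean k/197 against the observed k/196. For k = 167 (target 0.85) the gap is 167/196 − 167/197 = 0.004, or 0.4 points.

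| Target | 0.80 | 0.85 | 0.90 | 0.95 |
|---|---|---|---|---|
| Wilson coverage | 0.949 | 0.950 | 0.950 | 0.951 |
| Wald coverage | 0.947 | 0.945 | 0.941 | 0.927 |
| Wilson half-width | 0.056 | 0.050 | 0.042 | 0.030 |

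**4. Correction under Youden.** A bootstrap (200 resamples) that repeats the cut-off choice in each resample reduces the overstatement from 1.3-1.6 to 0.2-0.3 points (0.1 g/dL) and from 1.7-2.1 to 0.4-0.6 (continuous). A Wilson interval around the corrected value covered 0.950-0.959.

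**The case against.** The strongest reply is that no section mentions Youden. A pre-test meant to detect anaemia reliably could equally be set by a sensitivity target, and then the problem nearly disappears. This stands: the firm finding is the missing rule and interval, and every figure for overstatement is conditional.

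The cut-offs are also described tentatively, the mean bias is under half the planned half-width, and with SpHb recorded to 0.1 g/dL and Wilson or exact intervals the coverage loss is small. That limits the size but does not remove the point, because establishing cut-offs is a stated research question.

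Three stronger readings are tempting, and none is supported:

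- **That the reported sensitivity will be too high.** This holds only on average. Under Youden, observed exceeded true sensitivity in about 69-79% of simulated studies.
- **That precision is far worse than ±0.05 because reported sensitivity varies widely between repeat studies.** In setting A at 0.1 g/dL it ranged over 0.784-0.924, but mostly because the cut-off moves along the curve and true sensitivity moves with it. Observed minus true, which is what an interval must cover, ranged only from about −0.035 to +0.062.
- **That the bias amounts to a number of missed patients per 100,000.** It is a reporting bias: the same cut-off classifies the same patients either way. Moreover, section 7.1 gives the 14.1% for major hip, knee or spine surgery, whereas section 2 aims the pre-test at low-ASA patients having minor to intermediate surgery.

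**Conclusion.** The concern holds as an omission with a modest, conditional effect. The plan derives and evaluates the cut-off on one cohort without a rule, an interval or a correction, and its sample-size formula does not allow for that. With about 196 anaemic patients, sensitivity would be overstated on average by about 1-2 points under Youden and about 1-1.5 under closest-to-corner. Under Youden, nominal 95% coverage falls to about 85-92% (Wald) or 90-95% (Wilson or exact). A pre-stated target with a Wilson interval leaves coverage near nominal.

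At the planned 1500 patients (1500 × 0.141 = about 212 anaemic) the Youden overstatement is about 1.1-2.0 points. At the 8.0% prevalence quoted in section 7.1 for centres with a PBM programme (1392 × 0.080 = about 111 anaemic) it is about 2.0-3.1.

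The selection rule, SpHb resolution, Hb SD, normal distributions and interval type are assumptions; the documents give none of them. The change should be made, but the point does not call the sample size or the design into question.

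**What to change.** In 6.1, name the 0.85 as the sensitivity of SpHb for laboratory-defined anaemia.

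In 6.2, fix the cut-off selection rule before analysis, and report sensitivity and specificity at the chosen cut-off with Wilson or exact 95% intervals. Then:

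- If the rule is a sensitivity target, whose value is the investigators' to set, no further correction is needed. The ±0.05 of 6.1 applies only near 0.85.
- If the rule is Youden or another optimum, also report sensitivity corrected by a bootstrap that repeats the cut-off choice in every resample, with the bootstrap 95% range of the cut-off. Section 5.3 states: "All analyses will be performed, using this pseudonymized dataset, in IBM SPSS Statistics" 23. If the bootstrap cannot be run there, name the additional program in 5.3.

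Cost: one phrase in 6.1, about three sentences in 6.2 and, for the second option, a short script. No extra patients or measurements. Under an optimum rule the reported sensitivity falls by about 1-1.5 points. A high sensitivity target lowers specificity: in these settings, a target of 0.85 gave specificity between 7 points lower and 1 point higher than Youden, and a target of 0.95 gave 14-27 points lower.
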